4.3 Patient Randomization

Patients must meet all of the eligibility requirements listed in Section 3 prior to randomization. Treatment must begin \leq 7 working days from randomization.

An eligibility checklist has been appended as *an example* to the protocol and a usable version is available in separate study materials provided to the site. A confirmation of eligibility assessment by the investigator/site will be performed during the randomization process.

Information regarding stratification factors (performance status, measurable disease and prior chemotherapy) must be available at the time of randomization.

Once it is determined that a patient meets all eligibility requirements, the patient will be randomized to the study by site personnel using an electronic interactive web registration (IWR) system. Full information regarding registration and randomization procedures and guidelines can be found in the SRM provided to your site. All correspondence regarding patient randomization must be kept in the study records.

5 Treatment Plan

5.1 Administration Schedule

Note: 1 cycle = 28 days.

Patients must begin treatment within 7 working days of randomization.

Disease evaluations will occur after every 12 weeks, +/- 1 week (which corresponds to every 3 treatment cycles) and patients will be treated until disease progression, unacceptable toxicity or for a total duration of 12 cycles (Induction Phase). Patients with no evidence of progressive disease who remain on study after completing 12 cycles will be unblinded and proceed to the Continuation Phase. Patients in the Continuation Phase should continue to receive fulvestrant alone (if originally randomized to placebo) **or** in combination with everolimus (if originally randomized to everolimus) at the same dose and schedule. Disease evaluations will continue to occur after every 12 weeks (every 3 treatment cycles), +/- 1 week, and patients may continue treatment until disease progression is documented or unacceptable toxicity.

All patients will be followed for 30 days for toxicity after the last dose of study therapy (fulvestrant and/or everolimus/placebo) or until recovery from all toxicity (to \leq grade 1) attributed to study therapy, whichever is longer (or if $>$ grade 1, event must be permanent and stable).

See Sections 8.1 and 8.2 for information on study drug procurement, storage, preparation, handling and destruction information.

5.2 Dosing and Administration

5.2.1 Fulvestrant (Arm A and Arm B)

Induction Phase:

Cycle 1 (28 day cycle)

Patients will receive fulvestrant 500 mg IM (two-250 mg injections each dose) on day 1 and 15.

Note: *Cycle 1 is the only time fulvestrant is given on day 15. If patient previously received one cycle of fulvestrant (day 1 and day 15) prior to study entry as permitted in Inclusion Criteria #8, patient should receive fulvestrant 500 mg on day 1 only.*

Cycle 2, and thereafter (28 day cycles)

Patients will receive fulvestrant 500 mg IM (two-250 mg injections) on day 1 of all subsequent cycles for a maximum of 12 cycles.

Continuation Phase:

Patients with no evidence of disease progression after completing 12 cycles are unblinded and continue fulvestrant alone (if originally randomized to placebo) **or** in combination with everolimus (if originally randomized to everolimus) at the same dose and schedule until progression of disease or unacceptable toxicity.

Fulvestrant will be obtained from commercial pharmacy stock.

5.2.2 Everolimus or Placebo (Arm A and Arm B)

- The study drug everolimus/placebo will be self-administered (by the patients themselves). The local investigator will instruct the patient to take the study drug exactly as specified in the protocol. Everolimus/placebo should be administered orally once daily, preferably in the morning, at the same time every day with or without food. Everolimus/placebo tablets should be swallowed whole with a glass of water. The tablets must not be chewed or crushed. In cases where tablets cannot be swallowed, the tablets should be disintegrated in water just prior to being taken. Approximately 30 mL (2 tablespoons) of water should be put into a glass. The tablets should then be added and the contents stirred gently (for a maximum of 7 minutes) until the tablets are disintegrated. The contents should then be drunk. If the patient vomits after taking the study drug, they should not take another tablet that day. If the patient forgets to take the medication and remembers by 10 PM, they may take the dose. Otherwise, skip that dose and begin as usual the next day.
- Everolimus/placebo will be administered orally as once daily dose of 10 mg (two-5 mg tablets) continuously from study day 1 until progression of disease or unacceptable toxicity for 12 cycles. See Section 5.5 regarding duration of therapy (including guidelines for treatment beyond Cycle 12).
- If vomiting occurs, no attempt should be made to replace the vomited dose.
- All dosages prescribed and dispensed to the patient and all dose changes during the study must be recorded.
- PrECOG, or their designee, will be responsible for blinding, drug randomization, and management of the electronic interactive web registration (IWR) system. Both tablets will be blinded and identified by kit number only. The IWR system will assign the proper kit to the patient based on the patient randomization. Conditions for study drug will be described on the medication label.
- Both everolimus and placebo will be provided by Novartis. Everolimus is formulated as tablets for oral administration of 5 mg strength. Both placebo and everolimus tablets are blister-packed under aluminum foil in units of 10 tablets per blister card, which should be opened only at the time of administration as drug is both hygroscopic and light-sensitive.
- Dose modifications should be made prior to dose calculation at the beginning of each cycle and reasons recorded in source documents and on appropriate case report forms.

5.3 Dose Modifications and Toxicity Management

5.3.1 Dose Modifications General Guidelines for Everolimus/Placebo

CTCAE term (AE description) and grade: The descriptions and grading scales found in the revised NCI Common Terminology Criteria for Adverse Events (CTCAE) Version 4.0 will be utilized for AE reporting. All appropriate treatment areas should have access to a copy of the CTCAE Version 4.0. A copy of the CTCAE Version 4.0 can be downloaded from the CTEP web site (<http://ctep.cancer.gov>).

All appropriate treatment areas should have access to a copy of the CTEP CTCAE Version 4.0. (see Appendix E).

Dose modifications for all drugs will be made using the general guidelines below.

- All dose reductions are permanent. Fulvestrant will not be dose reduced.
- Regardless of the reason for holding any study drug treatment, the maximum allowable length of treatment interruption is \leq 3 weeks. If the delivery of any study drug due to toxicity is delayed for more than 3 weeks, that drug should be permanently discontinued.
- No more than 2 dose reductions for everolimus/placebo will be allowed. Further need for dose reduction will result in discontinuation of that drug.
- If dose is delayed due to toxicity, labs/toxicity should be reevaluated at least weekly until recovery to treatment levels, or as indicated in the dose modification tables.
- Patients who discontinue everolimus/placebo because of suspected everolimus-associated toxicity should continue treatment with fulvestrant alone until disease progression.
- In unusual circumstances where fulvestrant must be discontinued prior to disease progression due to intolerable fulvestrant-associated toxicity, the Medical Monitor should be contacted.

Table 5-0

Everolimus or Placebo Dose Level Modification Guidelines

	Everolimus/Placebo	Fulvestrant
Starting dose	10 mg daily (two- 5 mg tablets)	500 mg
Dose Level -1	5 mg daily	No reduction
Dose Level -2	5 mg every other day	No reduction

Table 5-1**Non-Hematological Criteria for Dose-Modification in Case of Suspected Everolimus or Placebo Related Adverse Events and Re-Initiation of Everolimus or Placebo Treatment**

Adverse Event	Action
Non Hematological	
Reactivation of HBV or HCV flare	Please refer to Table 5-4 and Table 5-5.
Non-Infectious Pneumonitis	Please refer to Table 5-6.
AST or ALT elevation Grade 1 (>ULN - 3.0x ULN) Grade 2 (>3.0 - 5.0x ULN)	Maintain current dose level.
AST or ALT elevation Grade 3 (>5.0 - 20.0 ULN)*	Interrupt everolimus administration until resolution to \leq grade 1 (or \leq grade 2 if baseline values were within the range of grade 2). If resolution occurs \leq 7 days, everolimus should be re-started at the dose level prior to interruption. If resolution takes >7 days, or if event recurs within 28 days, hold everolimus until recovery to \leq grade 1 or baseline grade/value and reintroduce everolimus at one dose level lower, if available.
AST or ALT elevation Grade 4 (>20x ULN)*	Interrupt everolimus administration until resolution to \leq grade 1 (or \leq grade 2 if baseline values were within the range of grade 2). If resolution occurs \leq 7 days, everolimus should be re-started at one dose level lower. If resolution takes >7 days, discontinue everolimus.
Intolerable Grade 2 mucositis (see Section 5.3.2.5)	Interrupt everolimus administration until resolution to \leq grade 1 or baseline grade/value. If resolution occurs within \leq 7 days, everolimus should be re-started at the dose level prior to interruption. If resolution takes >7 days, or if event recurs within 28 days, hold everolimus until recovery to \leq grade 1 or baseline grade/value and reintroduce everolimus at one dose level lower, if available. Patients will be withdrawn from the study if they fail to recover to \leq grade 1 or baseline grade/value within 21 days.
Grade 3 AE, except: hyperglycemia or hypertriglyceridemia or hypercholesterolemia (see Section 5.3.2.7)	Interrupt everolimus administration until resolution to \leq grade 1 or baseline grade/value. Reintroduce everolimus at one dose level lower, if available. Patients will be withdrawn from the study if they fail to recover to \leq grade 1 or baseline grade/value within 21 days.

Any other Grade 4	Hold everolimus until recovery to grade ≤ 1 or baseline value. Reintroduce everolimus at one dose level lower, if available.
Grade 3 or 4 clinical liver failure (asterixis or encephalopathy/coma)	Discontinue everolimus.
Recurrence of intolerable Grade 2 mucositis or Grade 3 event after dose reduction	Reduce dose to the next lower dose level, if available. The lowest possible dose level of everolimus is 5 mg every other day. Below this level, everolimus must be discontinued.
Recurrence of Grade 4 after dose reduction	Discontinue everolimus.
Any non-hematologic toxicity requiring interruption of everolimus for >21 days	Discontinue everolimus.

* Should HCV flare be confirmed, the guidelines for flare must take precedence (Table 5-5).

Table 5-2**Hematological Criteria for Dose-Modification in Case of Suspected Everolimus or Placebo Related Adverse Events and Re-Initiation of Everolimus or Placebo**

Adverse Event	Action
Hematological	
Grade 2 thrombocytopenia (platelets $<75, \geq 50 \times 10^9/L$)	No action.
Grade 3 thrombocytopenia (platelets $<50, \geq 25 \times 10^9/L$)	Interrupt everolimus until resolution to grade ≤ 1 If resolution occurs ≤ 7 days, reintroduce everolimus at the dose level prior to interruption. If resolution occurs >7 days, or event occurs within 28 days, reintroduce everolimus at one dose level lower, if available.
Grade 4 thrombocytopenia (platelets $<25 \times 10^9/L$)	Interrupt everolimus until recovery to grade ≤ 1 . Then reintroduce everolimus at one dose level lower, if available.
Grade 3 neutropenia or anemia (neutrophil $<1, \geq 0.5 \times 10^9/L$)	Interrupt everolimus until resolution to grade ≤ 1 or baseline value If AE resolution occurs ≤ 7 days, reintroduce everolimus at the same dose level. If AE resolution occurs >7 days, or event occurs within 28 days, reintroduce everolimus at one dose level lower, if available.

Grade 4 neutropenia or anemia	Interrupt everolimus until recovery to grade \leq 1 or baseline value. Reintroduce everolimus at one dose level lower, if available.*
Febrile neutropenia	Interrupt everolimus until resolution to grade \leq 1 (or baseline value) and no fever. Reintroduce everolimus at one dose level lower, if available.*
Recurrence of Grade 3 toxicity after dose reduction	Reduce dose to the next lower dose level, if available. The lowest possible dose level of everolimus is 5 mg every other day. Below this level, everolimus must be discontinued.
*Recurrence of Grade 4 toxicity (including febrile neutropenia) after dose reduction	Discontinue everolimus.
*Any hematologic toxicity requiring everolimus interruption for >21 days	Discontinue everolimus.

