5.6 Withdrawal of Patients from Study

Patients MUST be discontinued from study therapy AND be withdrawn from the study for the following reasons:

- Withdrawal of the patient's consent (patient's decision to withdraw for any reason)
- Termination of the study by PrECOG
- Any clinical adverse event, laboratory abnormality or intercurrent illness which, in the opinion of the investigator, indicates that continued participation in the study is not in the best interest of the subject
- Inability to comply with protocol
- Discretion of the investigator
- Disease progression (patient will continued to be followed for survival)

All subjects who discontinue treatment should comply with protocol specified follow-up procedures as outlined in Section 7.1.5.

If a subject is withdrawn before completing the study, the reason for withdrawal must be entered on the appropriate case report form.

6 Measurement of Effect

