Subjects who discontinue everolimus/placebo because of suspected everolimus-associated toxicity should continue treatment with fulvestrant alone until disease progression. In unusual circumstances where fulvestrant must be discontinued prior to disease progression due to intolerable fulvestrant-associated toxicity, the medical monitor should be contacted. All subjects who have discontinued protocol therapy will be followed for survival and for progression, even if protocol therapy was discontinued because of toxicity or for other reasons. All surviving subjects who have discontinued induction protocol therapy (fulvestrant and everolimus/placebo) for any reason will be followed for 30 days for study drug related (fulvestrant and/or everolimus/placebo) toxicities to  $\leq$  grade 1 (or if  $>$ grade 1, event must be permanent and stable).

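### Table 5-1 conflicts with itself on toxicity unresolved at 21 days: two rows withdraw the patient from the study, while the last row and the rest of the plan stop only everolimus/placebo and keep fulvestrant going

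*Protocol*

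**What the plan says.** Protocol 5.3.1 introduces its rules with "Dose modifications for all drugs will be made using the general guidelines below". Two of the bullets that follow matter here. One limits the consequence of a long interruption to the drug concerned: "If the delivery of any study drug due to toxicity is delayed for more than 3 weeks, that drug should be permanently discontinued". The other says what happens next: "Patients who discontinue everolimus/placebo because of suspected everolimus-associated toxicity should continue treatment with fulvestrant alone until disease progression". Protocol 5.5 repeats the second bullet, as do SAP 4.3 ("Subjects who discontinue everolimus/placebo because of suspected everolimus-associated toxicity should continue treatment with fulvestrant alone until disease progression") and SAP 4.4. SAP 4.4 also repeats the first.

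Table 5-1, in the same section, has a final row for "Any non-hematologic toxicity requiring interruption of everolimus for >21 days", and its only action is to stop everolimus. Two earlier rows, for intolerable Grade 2 mucositis and for Grade 3 events other than three metabolic ones, each end differently: "Patients will be withdrawn from the study if they fail to recover to" grade 1 or less, or baseline, within 21 days.

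Protocol 5.6 opens its list of withdrawal reasons with "Patients MUST be discontinued from study therapy AND be withdrawn from the study for the following reasons".

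**The concern.** A patient with a Grade 3 event or intolerable mucositis that has not resolved by day 22 meets two instructions. One removes her from the study. The other stops the tablets and leaves her on fulvestrant. Fulvestrant is the background treatment in both arms, and the planned strategy is to continue it to progression after everolimus/placebo is dropped for toxicity.

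Three things are at stake: early loss of protocol fulvestrant in patients who have not progressed, handling that depends on which line a site reads, and disposition tables (SAP 7.3.2 counts subjects who discontinue the study) that partly reflect that choice. The trigger events are expected mostly on everolimus. Protocol 5.3.2 cites grade 3 or 4 reactions in 39% versus 7% of patients in the renal-cell trial. Protocol 1.4.3.4 cites grade 3 or 4 stomatitis in 8% versus 1% in the trial of everolimus with exemestane.

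**Working it through.** **1. Is the trigger the same?** Both rows hold everolimus until recovery to grade 1 or baseline. A patient not recovered within 21 days has therefore been interrupted for more than 21 days, which is the trigger of the last row and of the 3-week bullet in 5.3.1. One patient meets all three.

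**2. Side by side, the action when that limit is passed:**

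| Place | Action |
|---|---|
| Table 5-1, intolerable Grade 2 mucositis | withdraw from study |
| Table 5-1, Grade 3 event (three metabolic exceptions) | withdraw from study |
| Table 5-1, last row | stop everolimus |
| 5.3.1 bullets, SAP 4.4 | stop the delayed drug; continue fulvestrant |
| 5.5, SAP 4.3 | continue fulvestrant after everolimus/placebo is stopped for toxicity |
| Table 5-2 (hematologic) | stop everolimus |
| Table 5-4 (hepatitis B) | stop study drug |
| Table 5-6 (pneumonitis, Grades 2 and 3) | stop everolimus |

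The first two rows are the outliers. They also reverse the order of severity. The row for other Grade 4 events has no withdrawal sentence, so a Grade 4 event unresolved at 21 days falls to the last row and stops everolimus only, while a Grade 3 event removes the patient from the study.

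**3. Is this left over from an amendment?** No. The change log shows that these rows were edited from 28 to 21 days, and the withdrawal sentence stands in the current table.

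**4. What does withdrawal entail?** Section 5.6 pairs it with stopping study therapy. Its adverse-event reason depends on the investigator's opinion, whereas the two rows are automatic.

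**5. Can the effect on the primary endpoint be sized?** The plan's event count reproduces. The hazard ratio is 5.4/9.2 = 0.587. With one-sided alpha 0.10 and 90% power, Freedman gives (1.2816 + 1.2816)² × (1.587/0.413)² = 97 events, and Schoenfeld gives 4 × (1.2816 + 1.2816)² / (ln 0.587)² = 93. The protocol states 98.

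The two inputs needed next are absent: the share of patients not recovered at 21 days, and the hazard after withdrawal. To see whether even the sign is fixed, assume that a share f of the everolimus arm (60 patients) stops everolimus at a uniform time in months 0 to 4 and none do on placebo. Afterwards those patients have k times the control hazard, where k = 1 means fulvestrant continues. Other settings: exponential PFS, uniform 12-month accrual, cut at month 24 (about 94 to 95 events), 12-weekly scans, everyone followed, unstratified logrank. The change in power due to the wording is the power at k minus the power at k = 1:

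| f | k = 0.75 | k = 1.5 | k = 2 |
|---|---|---|---|
| 3% (about 2 of 60) | .894 − .889 = +0.5 points | .883 − .891 = −0.8 | .879 − .891 = −1.2 |
| 7% (about 4 of 60) | .888 − .873 = +1.5 points | .856 − .876 = −2.0 | .843 − .876 = −3.3 |

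The k = 0.75 column comes from a run of 8,000 trials per cell and the others from 20,000, each set against its own k = 1 value. Both f and k are assumptions. The table shows that the sign depends on k. It does not bound the effect.

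**The case against.** The strongest reply is that the plan already makes its intent plain. The general guidelines cover all drugs, the last row covers any non-hematologic toxicity, and continuation of fulvestrant is stated four times. The two rows never mention fulvestrant, the table concerns everolimus/placebo dosing only, and 5.6 does not list non-recovery at 21 days among its reasons. The literal reading is therefore plausible but not the only one.

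Much of this stands. It identifies the intended rule, and it makes this a correction of wording and not a design flaw. It does not remove the conflict. Table 5-1 belongs to the same guidelines, nothing ranks bullets above rows, and 5.6 is where the protocol links withdrawal to stopping therapy.

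The reach is also limited. Pneumonitis, transaminase elevations, hepatitis, the three metabolic events and hematologic toxicity follow other rules. A physician could continue fulvestrant off protocol, since "Fulvestrant will be obtained from commercial pharmacy stock".

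A reader might infer three stronger claims that the documents do not support:

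- **That follow-up is lost.** Protocol 5.4, 5.5, 5.6 (closing lines), 7.1.5 and footnote m to the study table still require it after treatment stops. A site might misapply the word withdrawn, but the plan does not tell it to stop following the patient.
- **That the wording necessarily works against everolimus.** Section 5.3.4 requires withdrawal before other anticancer agents are given, so a withdrawn patient may start one. None of the PFS censoring rules (Protocol 6.1.6, SAP 5.3, SAP 7.7.2) censors at new therapy. The later hazard could lie below control.
- **That the renal trial's 7% versus 0% permanent discontinuation caps the rate.** Median everolimus exposure there was 141 days. Induction here runs up to 12 × 28 = 336 days, with a 21-day stopping rule that 5.3.2 does not describe for the renal trial. The rate here could be lower or higher.

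**Conclusion.** The inconsistency is real, sits in the current text, and should be corrected. Two rows of Table 5-1 prescribe study withdrawal where the last row, 5.3.1, 5.5 and SAP 4.3 and 4.4 stop only everolimus/placebo and keep fulvestrant. Read together with 5.6, following those rows ends protocol fulvestrant before progression, mainly on the everolimus arm. That departs from the planned treatment strategy and lets handling differ between sites.

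The rate of such events and the size and direction of any effect on PFS cannot be determined from the documents. It could dilute the treatment effect, be nil, or go the other way. The conclusion rests on the text alone. It needs none of the simulated figures and does not put the validity of the primary analysis in question.

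**What to change.** In both rows replace the withdrawal sentence with: *If not recovered to grade 1 or less, or baseline, within 21 days, permanently discontinue everolimus/placebo; continue fulvestrant until progression per 5.3.1 and 5.5, with 12-weekly tumor assessments.*

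Section 5.6 and the SAP need no change. The cost is a clarifying amendment to one sentence in two table rows, with no new visits, scans or data.

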5.3.2 Common Adverse Events Associated with Everolimus

The data described below reflect exposure to everolimus (n=274) and placebo (n=137) in a randomized Phase III study for the treatment of metastatic renal cell carcinoma. In total, 165 patients were exposed to everolimus 10 mg/day for \geq 4 months. The median age of patients was 61 years (range 27 to 85). The most common adverse reactions (incidence \geq 10%) were stomatitis, rash, fatigue, asthenia, diarrhea, anorexia, nausea, mucosal inflammation, vomiting, cough, peripheral edema, infections, dry skin, epistaxis, pruritus, and dyspnea. The most common grade 3-4 adverse reactions (incidence \geq 2%) were infections, stomatitis, fatigue, and pneumonitis.

The median duration of blinded study treatment was 141 days (range 19 to 451) for patients receiving everolimus and 60 days (range 21 to 295) for those receiving placebo. The rates of treatment-emergent adverse reactions resulting in permanent discontinuation were 7% and 0% for the everolimus and placebo treatment groups, respectively. Most treatment-emergent adverse reactions were grade 1 or 2 in severity. Grade 3 or 4 treatment-emergent adverse reactions were reported in 39% versus 7% of patients receiving everolimus and placebo, respectively. Deaths due to acute respiratory failure (0.7%), infection (0.7%), and acute renal failure (0.4%) were observed on the everolimus arm.

Everolimus has immunosuppressive properties and may predispose patients to bacterial, fungal, viral or protozoan infections, including infections with opportunistic pathogens. Localized and systemic infections, including pneumonia, other bacterial infections, invasive fungal infections, such as aspergillosis or candidiasis and viral infections including reactivation of hepatitis B virus, have been described in patients taking everolimus. Some of these infections have been severe (e.g. leading to respiratory or hepatic failure) and occasionally have had a fatal outcome.

Physicians and patients should be aware of the increased risk of infection with everolimus. Treat pre-existing infections prior to starting treatment with everolimus. While taking everolimus, be vigilant for symptoms and signs of infection; if a diagnosis of infection is made, institute appropriate treatment promptly and consider interruption or discontinuation of everolimus. If a diagnosis of invasive systemic fungal infection is made, discontinue everolimus and treat with appropriate antifungal therapy.

Reactivation of Hepatitis B (HBV) has been observed in patients with cancer receiving chemotherapy.⁵³ Sporadic cases of Hepatitis B reactivation have also been seen in this setting with everolimus. Use of antivirals during anti-cancer therapy has been shown to reduce the risk of Hepatitis B virus reactivation and associated morbidity and mortality.⁵⁴ A detailed assessment of Hepatitis B/C medical history and risk factors must be done for all patients at screening, with testing performed prior to the first dose of everolimus.

Hypersensitivity reactions manifested by symptoms including, but not limited to, anaphylaxis, dyspnea, flushing, chest pain or angioedema (e.g. swelling of the airways or tongue, with or without respiratory impairment) have been observed with everolimus.

Elevations of serum creatinine, usually mild, have been reported in clinical trials. Monitoring of renal function, including measurement of blood urea nitrogen (BUN) or serum creatinine, is recommended prior to the start of everolimus therapy and periodically thereafter.

Decreased hemoglobin, lymphocytes, platelets and neutrophils have been reported in clinical trials. Monitoring of complete blood count is recommended prior to the start of everolimus therapy and periodically thereafter.

The use of live vaccines and close contact with those who have received live vaccines should be avoided during treatment with everolimus.

Hypophosphatemia, hypomagnesaemia, hyponatremia and hypocalcaemia have been reported as serious adverse reactions. Electrolytes should be monitored in patients treated with everolimus.

Table 5-1 and Table 5-2 provide general recommendations for the management of patients, with suspected drug toxicities while on treatment with everolimus as single-agent therapy.

More detailed information regarding everolimus reported suspected toxicities and individual cases are provided in the Investigator's Brochure.

5.3.2.1 *Management of Hepatitis Reactivation/Flare*

In cancer patients with hepatitis B, whether carriers or in chronic state, use of antivirals during anticancer therapy has been shown to reduce the risk of hepatitis B virus (HBV) reactivation and associated HBV morbidity and mortality.⁵⁴

